8.2.5. Electrocardiograms

- All participants will undergo conventional 12-lead ECG using standardized equipment and electrode placement at the visits outlined in the SoA. Participants are to be in a semirecumbent position for at least 10 minutes prior to starting the tracing. During screening, a single ECG trace will be taken to assess entry eligibility.
- A qualified third-party vendor will read the ECGs and report the findings as normal, abnormal, or unable to evaluate.

- Before study intervention, if the ECG finding is clinically significant, the investigator must capture the finding in the medical history eCRF. After study intervention, if the pre-existing finding becomes worse and is clinically significant or the new ECG finding is clinically significant, the investigator must capture the adverse event in the adverse event eCRF. Hard copies of the ECG tracings will be kept in the study files at the investigator's site.

8.2.6. Hematology and Blood Chemistry

- See [Appendix 2](#) for the list of clinical laboratory tests to be performed and the SoA for the timing and frequency.
- Hematology and nonfasting blood chemistry assays will be performed by a central laboratory.
- During the Screening Period, the investigator or subinvestigator will assess the clinical significance of any values outside the reference ranges provided by the laboratory, and participants with abnormalities judged to be clinically significant will be excluded from the study.

8.2.7. Urine Pregnancy Test

Urine dipstick kits will be used to conduct pregnancy tests at the timepoints specified in the SoA, or more frequently at the investigator's discretion.

8.2.8. Suicidal Risk Monitoring

Suicidal risk monitoring is not applicable for this study.

8.3. Adverse Events and Serious Adverse Events

The definitions of an adverse event or SAE can be found in [Appendix 3](#).

Adverse events will be reported by the participant.

The investigator and any qualified designees are responsible for detecting, documenting, and recording events that meet the definition of an adverse event or SAE and remain responsible for following up adverse events that are serious, considered related to the study intervention or study procedures, or that caused the participant to discontinue the study intervention (see [Section 7](#)).

Adverse drug reactions for MT10109L have not been established.

The following expected adverse drug reactions are based on BOTOX clinical trial data for the treatment of GL and LCL (Table 8-1 and Table 8-2).

Table 8-1 **Expected Adverse Reactions for Treatment of Glabellar Lines**

Expected Adverse Reactions ^a	Incidence
Eyelid ptosis	3%
Facial pain	1%
Facial paresis	1%
Muscular weakness	1%

^a Data are based on BOTOX glabellar lines clinical trial data (BOTOX Cosmetic US Package Insert, 2017)

Table 8-2

Expected Adverse Reactions for Treatment of Lateral Canthal Lines

Expected Adverse Reactions ^a	Incidence
Eyelid oedema	1%

^a Data are based on BOTOX lateral canthal lines clinical trial data (BOTOX Cosmetic US Package Insert, 2017)

The adverse drug reactions of eyelid ptosis, facial pain, facial paresis, muscular weakness, and eyelid oedema with BOTOX usually are mild in severity, reversible, and have a low incidence. Therefore, no treatment for these reactions is recommended. If these reactions are moderate or severe, medical help should be sought as needed.

8.3.1. Time Period and Frequency for Collecting Adverse Event and Serious Adverse Event Information

For participants who received study intervention, all adverse events from the signing of the ICF until 30 days after the last study visit will be collected at the timepoints specified in the SoA

and as observed or reported spontaneously by study participants.

Medical occurrences that begin before the start of study intervention, but after obtaining informed consent will be recorded in the adverse event section of the eCRF.

All SAEs from the signing of the ICF until at least 12 weeks after the last administration of study intervention will be collected at the timepoints specified in the SoA (Section 1.3), and as observed or reported spontaneously by study participants.

All SAEs will be recorded and reported to the sponsor or designee within 24 hours, as indicated in Appendix 3. The investigator will submit any updated SAE data to the sponsor within 24 hours of it being available.

Investigators are not obligated to actively seek adverse event or SAE information after conclusion of the study participation. However, if the investigator learns of any SAE, including a death, at any time after a participant has been discharged from the study, and he/she considers the event to be reasonably related to the study intervention or study participation, the investigator must promptly notify the sponsor.

The method of recording, evaluating, and assessing causality of adverse events and SAEs and the procedures for completing and transmitting SAE reports

8.3.2. Method of Detecting Adverse Events and Serious Adverse Events

Care will be taken not to introduce bias when detecting adverse events and/or SAEs. Open-ended and nonleading verbal questioning of the participant is the preferred method to inquire about adverse event occurrences.

MT10109L

8.3.3. Follow-up of Adverse Events and Serious Adverse Events

After the initial adverse event/SAE report, the investigator is required to proactively follow each participant who received study intervention at subsequent visits/contacts. All TEAEs/SAEs, including AESIs [REDACTED] will be followed until resolution, stabilization, the event is otherwise explained, or the participant is lost to follow-up (as defined in [Section 7.3](#)).

The investigator is obligated to perform or arrange for the conduct of supplemental measurements and/or evaluations as medically indicated or as requested by the sponsor to elucidate the nature and/or causality of the adverse event or SAE as fully as possible. This may include additional laboratory tests or investigations, histopathological examinations, or consultation with other health care professionals.

If a participant dies during participation in the study or during a recognized follow-up period, the investigator will provide the sponsor with a copy of any postmortem findings including histopathology.

New or updated information will be recorded in the originally completed eCRF.

The investigator will submit any updated SAE data to the sponsor within 24 hours of receipt of the information.

8.3.4. Regulatory Reporting Requirements for Serious Adverse Events

- Prompt notification by the investigator to the sponsor of an SAE is essential so that legal obligations and ethical responsibilities towards the safety of participants and the safety of a study intervention under clinical investigation are met.
- The sponsor has a legal responsibility to notify both the local regulatory authority and other regulatory agencies about the safety of a study intervention under clinical investigation. The sponsor will comply with country-specific regulatory requirements relating to safety reporting to the regulatory authority, IRBs/ IECs, and investigators.
- Investigator safety reports must be prepared for SUSARs according to local regulatory requirements and sponsor policy and forwarded to investigators as necessary.
- An investigator who receives an investigator safety report describing an SAE or other specific safety information (eg, summary or listing of SAEs) from the sponsor will review and then file it along with the investigator's brochure and will notify the IRB/IEC, if appropriate according to local requirements.

8.3.5. Pregnancy

- Urine pregnancy testing will be conducted for women of childbearing potential prior to each study intervention and at the study exit visit. See [Appendix 7](#) for detailed information on definition of women of childbearing potential, use of contraceptives, and pregnancy.
- To minimize the risk of pregnancy, all women of childbearing potential must agree to use a highly effective or acceptable contraception method ([Appendix 7](#)) consistently and correctly

MT10109L

throughout the duration of the study. For participants of childbearing potential in Germany, only highly effective contraception methods are allowed for this study.

- Women who test positive for urine pregnancy test will NOT receive further treatment and will be discontinued from the study.
- Women who test positive for urine pregnancy test should complete end-of-study procedures and be followed up for pregnancy outcome.
- Any termination of pregnancy will be reported, regardless of fetal status (presence or absence of anomalies) or indication for the procedure.
- If a pregnancy is reported, the investigator should inform the sponsor within 24 hours of learning of the pregnancy and should follow the procedures outlined in [Appendix 7](#).
- Abnormal pregnancy outcomes (eg, spontaneous abortion, fetal death, stillbirth, congenital anomalies, ectopic pregnancy) or genetic abnormalities (whether leading to an elective abortion or not) are considered SAEs.

8.3.7. Medication Errors

Medication error refers to any unintended error in the dosing and/or administration of the study intervention as per instructions in the protocol. Medication errors generally fall into 4 categories as follows:

- Wrong study intervention
- Wrong dose (including dosing regimen, strength, form, concentration, amount)
- Wrong route of administration
- Wrong participant (ie, not administered to the intended participant)

Medication errors include occurrences of overdose and underdose of the study intervention.

Overdose: Unintentional administration of a quantity of the study intervention given per administration that is above the maximum recommended dose according to the protocol for the study intervention or comparator as applicable. See [Section 8.4](#) for information of treatment of overdose.

Underdose: Unintentional administration of a quantity of the study intervention given per administration that is under the minimum recommended dose according to the protocol.

8.4. Treatment of Overdose

Overdose of MT10109L is a relative term and depends upon dose, site of injection, and underlying tissue properties. Signs and symptoms of overdose are likely not to be apparent immediately postinjection. Excessive doses may produce local, or distant, generalized and profound neuromuscular paralysis.

Because MT10109L is administered as injections by physicians, for this study, the chance of overdose is extremely low. Should accidental injection or oral ingestion occur or overdose be suspected, the participant should be medically monitored for up to several weeks for progressive signs or symptoms of systemic muscular weakness that could be local or distant from the site of injection, which may include ptosis, diplopia, dysphagia, dysarthria, generalized weakness, or respiratory failure. For GL or LCL, eyelid ptosis, diplopia, or vision blurred are known local effects of the toxin. These participants should be considered for further medical evaluation and appropriate medical therapy immediately instituted, which may include hospitalization.

If the musculature of the oropharynx and esophagus is affected, aspiration may occur, which may lead to development of aspiration pneumonia. If the respiratory muscles become paralyzed or sufficiently weakened, intubation and assisted respiration may be necessary until recovery takes place. Supportive care could involve the need for a tracheostomy and/or prolonged mechanical ventilation, in addition to other general supportive care.

In the event of an overdose, the investigator should educate the participant, monitor the course of overdose, contact the medical safety physician as needed, document the quantity of the excess dose, associated adverse events as well as the duration of the overdose in the eCRF.

8.5. Pharmacokinetics

Pharmacokinetic parameters are not evaluated in this study.

8.6. Pharmacodynamics

Pharmacodynamic parameters are not evaluated in this study.

8.7. Genetics

Genetics are not evaluated in this study.

CONFIDENTIAL

Protocol MT10109L-005 AMD 4

MT10109L

8.9. Medical Resource Utilization and Health Economics

Medical resource utilization and health economics parameters are not evaluated in this study.

[figure not shown]
9. Statistical Considerations

9.1. Statistical Hypotheses

For US FDA:

The primary efficacy analysis will be performed on the ITT population, which consists of all randomized participants. The following hypotheses will be used to compare MT10109L 20 U and placebo:

- Null hypothesis: MT10109L 20 U and placebo are equally effective in reducing GL severity at maximum frown as measured by the proportion of responders with ≥ 2 -grade improvement from baseline based on both the investigator- and participant-rated FWS at Day 30.
- Alternative hypothesis: MT10109L 20 U and placebo are not equally effective in reducing GL severity at maximum frown as measured by the proportion of responders with ≥ 2 -grade improvement from baseline based on both the investigator- and participant-rated FWS at Day 30.

MT10109L

9.2. Sample Size Determination

Approximately 375 participants will be randomized into the study

9.3. Populations for Analyses

Primary and secondary efficacy analyses for US FDA will be performed on the ITT population, consisting of all randomized participants.

The safety analyses will be based on the safety population, which will include all participants who receive at least 1 injection of study intervention. All safety analyses will be performed with participants analyzed by their actual treatment or regimen received.

MT10109L

9.4. Statistical Analyses

The SAP will be developed and finalized before database lock and unblinding and will describe the participant populations to be included in the analyses, and procedures for accounting for missing, unused, and spurious data. This section is a summary of the planned statistical analyses of the primary, secondary, and exploratory endpoints.

9.4.1. Efficacy Analyses

9.4.1.1. Primary Efficacy Endpoints

For the US FDA, the composite efficacy endpoints are the proportion of participants with ≥ 2 -grade improvement from baseline on the FWS according to investigator and participant assessments of GL severity at maximum frown at Day 30 using the ITT population after the single IM injection of MT10109L or placebo in the GL.

9.4.1.2. Primary Analyses

The primary efficacy analysis will be based on the comparison of GL efficacy for MT10109L 20 U versus placebo at the primary timepoint of Day 30 of the first treatment period. The evaluation of the equality of the proportions of responders will be based on CMH test stratified by investigator-assessed baseline GL severity at maximum frown. Relative risk and 95% CI for relative risk will be presented. Missing values will be imputed up to Day 180 using multiple imputation methods.

9.4.1.4. Secondary Analyses

All secondary variables will be evaluated for all study visits with the prespecified primary timepoint given below, except for duration of treatment effect.

9.4.1.5. Exploratory Efficacy Endpoints

[REDACTED] exploratory efficacy endpoints will be performed on the ITT population.

MT10109L

9.4.1.6. Exploratory Efficacy Analyses

The proportion of responders will be analyzed using the CMH test

9.4.2. Safety Analyses

The safety analysis will be performed using the safety population and are fully defined in the SAP. The safety parameters will include:

- Adverse events
- [REDACTED]
- [REDACTED]
- Vital signs
- Electrocardiogram
- Immunogenicity analyses
- Hematology and chemistry laboratory tests

9.4.2.1. Adverse Events

An adverse event will be considered a TEAE if:

- The adverse event began on or after the date of the first dose of study intervention; or
- The adverse event was present before the date of the first dose of study intervention, but increased in severity or became serious on or after the date of the first dose of study intervention

An adverse event that occurs more than 30 days after study exit will not be counted as a TEAE.

An adverse event will be considered a TESAE if it is a TEAE that additionally meets any SAE criteria.

The number and percentage of participants reporting TEAEs in each study intervention group will be tabulated by system organ class and preferred term and by system organ class, preferred term, and severity.

The number and percentage of participants reporting treatment related TEAEs in each study intervention group will be tabulated by system organ class and preferred term.

If more than 1 adverse event is coded to the same preferred term for the same participant, the participant will be counted only once for that preferred term using the most severe and most related occurrence for the summarizations by severity and by relationship to study intervention.

The number and percentage of participants reporting TEAEs that are included in the PDSOT term list will be tabulated by study intervention. The PDSOT term list will be provided by the MSP.

MT10109L

The PDSOT will be reviewed by the MSP in a timely fashion for monitoring severity, frequency, and trending.

Summary tables will be provided for participants with SAEs and participants with adverse events leading to discontinuation if 5 or more participants reported such events. Listings of all adverse events, SAEs, and adverse events leading to discontinuation by participant will be presented.

The definitions of an adverse event and SAE can be found in [Appendix 3](#).

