- During the retreatment period (from Day 180 through Day 330), participants who meet retreatment criteria will receive up to 2 blinded interventions of the same study intervention received in the first period (MT10109L 20 U, 44 U, or placebo).
[REDACTED]
- Participants who complete the study will have an exit visit at Day 360.
[REDACTED]

MT10109L

Number of Participants:

Approximately 375 participants will be enrolled in order to have 318 participants complete the study based on an anticipated dropout rate of 15%.

Number of Sites:

Approximately 16 global sites

Intervention Groups and Study Duration:

- The total duration of study participation for each participant is approximately 12 months (Day 1 randomization/treatment to end of study/Day 360). Participants will attend the following visits:
 - Screening (up to 28 days before Day 1)
 - Randomization and treatment (Day 1)
 - Follow-up visits on Days 7 and 14 after each intervention
 - Monthly (Days 30, 60, 90, 120, 150, 180, 210, 240, 270, 300, and 330)
 - Exit (Day 360 [completion] or early exit)
- On Day 1, participants will receive intramuscular injections of MT10109L 20 U (MT10109L in GL area, placebo in LCL area), MT10109L 44 U (20 U in GL area and 24 U in LCL area), or placebo (placebo in both GL and LCL areas).
- During the retreatment period (from Day 180 through Day 330), participants who meet retreatment criteria will receive up to 2 blinded interventions of the same study intervention received in the first period (MT10109L 20 U, 44 U, or placebo).

Data Monitoring Committee: No

Approval Date: 30-Sep-2020 22:55:16 (GMT)

2. Introduction

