4.1. Overall Design

- This is a multicenter, randomized, double-blind, placebo-controlled, parallel-group Phase 3 study conducted across approximately 16 global sites to evaluate the safety and efficacy of MT10109L in treating GL with or without concurrent treatment of LCL. Participants may receive up to 3 interventions.
- Participants are adults ≥ 18 years of age with moderate to severe GL at maximum frown (assessed by both the investigator and participant using the FWS [investigator and participant ratings must be the same for GL]) and bilaterally symmetrical moderate to severe LCL at maximum smile (same grade on both sides of the face as assessed by the investigator only).

MT10109L

- Participants who complete the study will have an exit visit at Day 360.
- The total duration of study participation for each participant is approximately 12 months (Day 1 randomization/treatment to end of study/Day 360). Participants will attend the following visits:
 - Screening (Day -28 to Day -1)
 - Randomization and treatment (Day 1)
 - Follow-up visits on Days 7 and 14 after each intervention
 - Monthly (Days 30, 60, 90, 120, 150, 180, 210, 240, 270, 300, and 330)
 - Exit (Day 360 [completion] or early exit)

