4.4. End of Study Definition

The end of the study is defined as the date of the last scheduled procedure shown in the SoA for the last participant in the study globally.

A participant is considered to have completed the study if he/she has completed all phases of the study including the last scheduled procedure shown in the SoA.

5. Study Population

Adult participants in the current study have moderate to severe GL at maximum frown and moderate to severe LCL at maximum smile as specified in Section 5.1.

Prospective approval of protocol deviations to recruitment and enrollment criteria, also known as protocol waivers or exemptions, is not permitted.

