11.1 ADVERSE EVENTS

AEs will be coded from the verbatim text into preferred term (PT) and the primary system organ class (SOC) by using the MedDRA dictionary. In general, adverse events (AEs) data will be analyzed and presented for:

1. TEAEs: An adverse event will be considered a treatment-emergent adverse event (TEAE) if: 1) The adverse event began on or after the date of the first study intervention; or 2) The adverse event was present before the date of the first study intervention, but increased in severity or became serious on or after the date of the first study intervention. An adverse event that occurs more than 30 days after the study exit will not be counted as a TEAE.

[REDACTED]

Per case report form instructions, a new AE record will be created with a new AE onset date for any AE that worsens. Therefore, TEAEs can simply be identified as those AEs with a recorded onset date on or after the date of the first study intervention and within 30 days after the study exit.

In each of the analysis periods (entire study, or by treatment cycle), a specific TEAE will only count once per participant, associated with its worst severity during the time period of interest. Unless stated otherwise, the method of analyses described in this section will be applied to each of the screening/baseline and study intervention periods.

Adverse events will be summarized by treatment group for the entire study and by treatment cycle in descending order of incidence rate.

Three incidence rate tables will be presented for summarizing all TEAEs:

- 1) by descending order of incidence rate
- 2) by primary SOC and PT
- 3) by SOC, PT, and severity.

Serious TEAE and treatment-related TEAE will be summarized by primary SOC and PT for entire study. Treatment-related TEAE will also be summarized by related to study drug or related to study procedure. TEAE leading to study discontinuation will be summarized by primary SOC and PT for entire study

A participant listing will be generated for all AEs, SAEs, treatment-related AEs and AEs leading to study discontinuation.

All AEs associated with PDSOT will be tabulated by SOC, PT, and treatment group; in addition, all PDSOT AEs will be listed by participant.

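### The treatment-emergent window ends before the protocol's 12-week SAE collection window for injections after Day 306 and for exits less than 54 days after an injection; a minor mismatch to reconcile

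*Protocol*

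**What the plan says.** **Analysis window.** Protocol 9.4.2.1: "An adverse event that occurs more than 30 days after study exit will not be counted as a TEAE". SAP 11.1: "An adverse event that occurs more than 30 days after the study exit will not be counted as a TEAE". The SAP then gives a programming shortcut that identifies TEAEs by onset date, with the same upper limit of 30 days after exit. Serious events inherit the limit, because in Protocol 9.4.2.1 "An adverse event will be considered a TESAE if it is a TEAE that additionally meets any SAE criteria".

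**Collection windows.** Protocol 8.3.1 sets two. For events in general, "all adverse events from the signing of the ICF until 30 days after the last study visit will be collected". For serious events, "All SAEs from the signing of the ICF until at least 12 weeks after the last administration of study intervention will be collected". The same section says that investigators need not actively look for events once participation has ended, although they must report related SAEs that they learn of.

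**Timing of injections and exit.** The synopsis says: "During the retreatment period (from Day 180 through Day 330), participants who meet retreatment criteria will receive up to 2 blinded interventions". Protocol 4.1 says: "Participants who complete the study will have an exit visit at Day 360". It also allows early exit.

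**Outputs.** SAP 11.1 tabulates serious TEAEs by system organ class and preferred term. Protocol 9.4.2.1 plans a summary table of SAEs, not worded as treatment-emergent only, if 5 or more participants have such events. Both documents list all AEs and all SAEs by participant.

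**The concern.** The general AE collection window and the TEAE rule agree: both close 30 days after the last visit or exit. The separate SAE window does not fit that rule, because it starts from the last injection. If someone is injected late, or leaves soon after an injection, the SAE window can still be open when the treatment-emergent window has closed. An SAE with onset in between must be collected, yet by rule it is neither a TEAE nor a TESAE.

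At stake is the completeness of the serious-event comparison in two groups: late retreatments and early leavers. Both bear on the hypothesis in Protocol 4.1.1 that safety is acceptable after single treatment and retreatment. SAEs are likely to be few, so one omitted event could change a between-group count.

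**Working it through.** The plan gives no figure of its own for this gap. The only related figure that can be recomputed is enrolment: 318 / (1 − 0.15) = 374.1, rounded up to 375. It reproduces, and it implies 375 − 318 = 57 non-completers.

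**Inputs**
- TEAE/TESAE cut-off: exit + 30 days (Protocol 9.4.2.1, SAP 11.1)
- Minimum end of SAE collection: last injection + 12 × 7 = 84 days (Protocol 8.3.1)
- Latest injection: Day 330 (Protocol 1.1)
- Exit for completers: Day 360 (Protocol 4.1)

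**Formula.** Gap = max(0, (last injection + 84) − (exit + 30)). If d is the number of days from last injection to exit, this is max(0, 54 − d).

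**Completers.** The cut-off is 360 + 30 = Day 390. Break-even is 390 − 84 = Day 306.

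| Last injection | SAE window ends (minimum) | Gap |
|---|---|---|
| Day 180 | Day 264 | 0 |
| Day 240 | Day 324 | 0 |
| Day 270 | Day 354 | 0 |
| Day 300 | Day 384 | 0 |
| Day 306 | Day 390 | 0 |
| Day 320 | Day 404 | 14 days |
| Day 330 | Day 414 | 24 days (Days 391 to 414) |

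Among the monthly visits, only a Day 330 injection opens a gap for a completer: 24 / 84 = 29% of the 12-week window.

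**Early exits**

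| Days from last injection to exit | Gap |
|---|---|
| 0 | 54 days |
| 7 | 47 days |
| 14 | 40 days |
| 30 | 24 days |
| 54 or more | 0 |

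**How many SAEs.** The documents give no SAE rate, no distribution of retreatment days and no timing of dropout, so only a bound under assumptions is possible. Suppose that all 318 completers were injected on Day 330 and all 57 non-completers left on the day of an injection:
- Completers: 318 × 24 / 365.25 = 20.9 person-years
- Non-completers: 57 × 54 / 365.25 = 8.4 person-years
- Total: 29.3 person-years

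At an assumed 1 to 5 SAEs per 100 person-years, this is 29.3 × 0.01 = 0.3 to 29.3 × 0.05 = 1.5 SAEs over the whole trial. The real exposure must be far smaller, since that scenario is not realistic. The bound takes collection to stop at 84 days. The protocol sets 12 weeks as a minimum, so the gap lengthens wherever collection continues.

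**The case against.** The 30-day rule has a sound basis. It matches the period in which serious and non-serious events are both collected. Extending it for SAEs alone counts serious events over a longer period than non-serious ones. This stands, and it is a reason to leave the general TEAE tables alone.

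Most participants are unaffected. Every completer last injected by Day 306 has no gap within the 12-week minimum. The 15% dropout figure does not measure the number affected, because only those who leave less than 54 days after an injection count. This also stands.

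Capture in the gap is uncertain, because active follow-up after exit is not required and some participants may refuse further use of their information. This is partly right. Protocol 8.3.1 nevertheless says that SAEs in the 12-week window are collected. Protocol 8.3.5 also follows pregnancies to outcome after discontinuation and classes abnormal outcomes as SAEs, so serious events can reach the database well after exit.

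The schedule of activities is not in the published text, and part of SAP 11.1 is redacted. Either could narrow the gap. The visible text fixes completer exit at Day 360 and contains nothing that reconciles the windows.

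A reader might infer two stronger points that the documents do not support:
- **That these SAEs never enter the safety comparison.** They remain in the listings of both documents, and the wording of the protocol's SAE summary table would admit them if its threshold of 5 participants is met.
- **That the study or database closes before these SAEs arrive.** Protocol 4.4 says "The end of the study is defined as the date of the last scheduled procedure shown in the SoA" for the last participant globally. That is a single trial-level date, not a data cut-off, and no passage places database closure at Day 360.

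**Conclusion.** The mismatch is real, narrow and minor. For completers last injected on Days 307 to 330, up to 24 days of required SAE collection fall outside the treatment-emergent window. For participants who exit less than 54 days after an injection, up to 54 days do. SAEs with onset there are excluded from the TESAE counts and from the SAP's serious-TEAE table, but not from reporting altogether.

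The day counts follow directly from the stated windows, with exit at Day 360 and injections no later than Day 330. The number of events rests on assumed SAE rates and an extreme exposure scenario, and even then it is no more than about one or two. The share of participants affected cannot be derived from the published text. This does not threaten the primary efficacy analysis or the overall safety reporting. It is worth correcting because required safety data should not drop out of the serious-event table through an unreconciled definition.

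**What to change.** In Protocol 9.4.2.1 and SAP 11.1, do one of the following:
1. Give serious events their own cut-off: the later of 30 days after study exit and 12 weeks after the last study intervention. Amend the TESAE definition so that it no longer depends on the 30-day TEAE limit, and change the SAP's onset-date shortcut to match.
2. State that the serious-event summary table includes every SAE collected under Protocol 8.3.1, whatever its TEAE status.

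Keep the general TEAE tables on the 30-day rule. Show SAEs from the extended window only in the serious-event table, with a footnote giving the window used. Settle the rule before unblinding.

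The cost is a sentence or two in each document and a small programming change. No visit or procedure is added, because collection is already specified. The price is that serious events are counted over a slightly longer period than non-serious ones; the footnote and the restriction to one table keep that visible. Serious-event counts may rise slightly.
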